9.2.2. Adverse Events of Special Interest

The number of participants who experienced TEAEs of special interest listed below will be summarized by maximum severity.

- Colitis
- Diarrhea
- Exfoliative dermatitis

- Febrile neutropenia
- Rash
- Intestinal perforation
- Pneumonitis
- Pneumonia
- PJP infection
- CMV infection
- Herpes simplex
- Varicella zoster virus infection

The time to onset of a TEAE is defined as the interval between the date of first dose of study drug and the date of the first occurrence of a TEAE. Participants who have not experienced a TEAE at the time of analysis will be right-censored at the earlier of 30 days after the last dose date and date of last study visit through the end of safety follow-up. If participants have missing or partial last dose dates of study drug or onset date of a TEAE, the partial or missing dates will be handled using the rules explained in Section 4.1.4.

Summaries of time to onset of new or worsening Grade 3 or higher AEs will be provided using descriptive statistics and the life-table method for rash, colitis, diarrhea, febrile neutropenia, pneumonia, herpes simplex, and varicella zoster virus infection. In addition, summaries of time to onset of new or worsening AEs of any grade will be provided using descriptive statistics and the life-table method for colitis, diarrhea, exfoliative dermatitis, intestinal perforation, pneumonia, pneumonitis, PJP infection, CMV infection, herpes simplex, and varicella zoster virus infection. Kaplan-Meier plots of time to onset of new or worsening Grade 3 or higher AEs will be provided for rash, colitis, and diarrhea. In addition, Kaplan-Meier plots of time to onset of new or worsening AEs of any grade will be provided for colitis and diarrhea.

Descriptive statistics of time to onset of these TEAEs of special interest are based on all participants who have experienced a TEAE at the time of analysis. To summarize these TEAEs of special interest using the life-table method, the effective sample size is defined as the number of participants at the beginning of the interval minus half the participants censored in the interval. The conditional proportion is calculated as the number of first events divided by the effective sample size in the interval.

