The longest duration of a TEAE of any grade is defined as the longest interval between the date of occurrence of a TEAE and the date of resolution. The longest duration of a Grade 3 or higher TEAE is defined as the longest interval between the date of occurrence of a Grade 3 or higher TEAE and the date of improvement to Grade 2 or lower. If participants have missing or partial onset/end date of a TEAE, the partial or missing dates will be handled using the rules explained in Section 4.1.4. Participants who have missing end date of a TEAE at the time of analysis will be right-censored using the following algorithm:

- If the TEAE is serious, then the participant will be censored at the earlier date of data cutoff, study discontinuation and death.

- If the TEAE is not serious,
 - If the participant is ongoing with study treatment, then the participant will be censored at the data cutoff date, OR
 - If the participant discontinued treatment, then the participant will be censored at date of safety follow-up visit, or 35 days after the end of treatment visit (or after the last dose if the end of treatment visit was not performed), whichever is later; the censored date will be truncated by the earlier date of data cutoff, study discontinuation, and death if beyond.

Longest duration of new or worsening Grade 3 or higher colitis, diarrhea, rash, and febrile neutropenia will be summarized. In addition, longest duration of new or worsening AEs of any grade will be summarized for colitis, diarrhea, and rash.

The total number of participants whose TEAE of any grade resolved or whose Grade 3 or higher TEAE improved to Grade 2 or lower, and the number of participants censored will be summarized. The Kaplan-Meier estimate of median time to resolution/improvement and its 95% CIs will be provided, with the CIs calculated using the generalization of Brookmeyer and Crowley's method (1982) with log-log transformation (Klein and Moeschberger 1997). Resolution/improvement rates at selected timepoints will also be provided with 95% CIs calculated using Greenwood's formula to estimate the standard error.

TEAEs of special interest to be summarized may be adjusted based on emerging data.

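### Kaplan-Meier resolution rates for adverse events of special interest censor at death, so they sit at or above the proportion of participants whose event actually resolves

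*SAP*

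**What the plan says.** SAP 9.2.2 defines the longest duration of an event of any grade as "the longest interval between the date of occurrence of a TEAE and the date of resolution". For Grade 3 or higher events the endpoint is "the date of improvement to Grade 2 or lower". The Grade 3 or higher summaries cover colitis, diarrhea, rash and febrile neutropenia; the any-grade summaries cover the first three.

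The censoring rule opens with "Participants who have missing end date of a TEAE at the time of analysis will be right-censored using the following algorithm". It has two branches:

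- Serious events: "then the participant will be censored at the earlier date of data cutoff, study discontinuation and death".
- Non-serious events after treatment has stopped: a date tied to the safety follow-up visit or 35 days after end of treatment, but "the censored date will be truncated by the earlier date of data cutoff, study discontinuation, and death if beyond".

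The estimators follow: "The Kaplan-Meier estimate of median time to resolution/improvement and its 95% CIs will be provided", and "Resolution/improvement rates at selected timepoints will also be provided with 95% CIs calculated using Greenwood's formula to estimate the standard error". The numbers resolved or improved and the number censored are also to be summarized. The section names no competing-risk estimator, no rule for participants who die unresolved, and no sensitivity analysis.

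**The concern.** Kaplan-Meier treats a censored participant as having the same later chance of the event as those who remain at risk. That is reasonable for a data cutoff. It cannot hold for someone who died with colitis still present. Censoring that participant passes their weight to the survivors, some of whom go on to resolve. The Grade 3 or higher set also includes Grade 5, which Protocol 8.1.2 defines as death due to the event and which can never improve to Grade 2.

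SAP 11.2 (Amendment 1) says the duration summaries were added to describe how long class-effect toxicities last. A reader will take the timepoint rates as the proportion of participants who recovered. If some died unresolved, the toxicity will look more reversible than it was.

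**Working it through.** The plan states no figure for time to resolution, so there is nothing to reproduce. The direction follows from the estimator; the size needs assumptions.

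**Inputs from the documents.** The censoring dates, the endpoint and the Kaplan-Meier estimator are those in SAP 9.2.2.

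**Assumed inputs (not in the documents).** Constant hazards; a Kaplan-Meier median of 14 days; a share f of participants with the event who eventually die unresolved, from 2% to 20%.

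**Formulas.** With resolution hazard Lr and hazard of death while unresolved Ld:

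- Lr = ln 2 / 14 = 0.0495 per day, and f = Ld / (Lr + Ld), so Ld = Lr × f / (1 − f).
- One minus Kaplan-Meier, deaths censored: 1 − exp(−Lr × t).
- Cumulative incidence, death competing: (1 − f) × [1 − exp(−(Lr + Ld) × t)].

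**Example, f = 10%, day 90.** Ld = 0.0495 × 0.1 / 0.9 = 0.0055. Kaplan-Meier gives 1 − exp(−4.456) = 98.8%. Cumulative incidence is 0.9 × [1 − exp(−4.951)] = 89.4%.

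| Share dying unresolved | Day 28: Kaplan-Meier | Day 28: cumulative incidence | Day 90: Kaplan-Meier | Day 90: cumulative incidence | Median from cumulative incidence (Kaplan-Meier 14.0 days) |
|---|---|---|---|---|---|
| 2% | 75.0% | 74.2% | 98.8% | 97.0% | 14.1 days |
| 5% | 75.0% | 72.9% | 98.8% | 94.1% | 14.3 days |
| 10% | 75.0% | 70.7% | 98.8% | 89.4% | 14.7 days |
| 20% | 75.0% | 65.9% | 98.8% | 79.7% | 15.8 days |

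The day-90 gaps are 1.8, 4.7, 9.4 and 19.1 points. The day-28 gaps are 0.8, 2.1, 4.3 and 9.1 points.

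**Small-sample check.** Suppose every survivor eventually resolves and the last person at risk is a resolver. The final Kaplan-Meier factor is then 1 − 1/1 = 0, and the reported rate is 100% whatever the number of deaths. With 20 events and 1, 2 or 3 deaths, the true proportions are 19/20 = 95%, 18/20 = 90% and 17/20 = 85%. At day 28, in constructed samples of 10, 20 and 30 events with up to 3 deaths, the gap ran from 0 to 10 points. The largest was 40% against 30%, with 10 events and 3 early deaths.

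**End dates for fatal events.** Censoring applies only when the end date is missing. Protocol 8.1.2 asks for an end date unless the event is unresolved at final follow-up, and lists fatal as an outcome. It does not say what end date a fatal event receives. SAP 4.1.4 imputes partial end dates and caps them at study discontinuation or death. No stated rule prevents an end date equal to the death date from being read as resolution. If it were so read, with f = 10%, the day-28 rate would be 1 − exp(−0.0550 × 28) = 78.6% against a true 70.7%, further off than censoring (75.0%).

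**The case against.** The strongest reply is that the information needed to see the problem is already planned. SAP 9.2.2 reports the numbers resolved and censored beside the curve, and fatal events have their own tables (SAP 9.2.3) and listing (SAP Appendix A). With 8 resolved and 2 censored out of 10, a reader could work out 80%. SAP 9.2.3 also allows a listing when 10 or fewer participants would appear in a table. These summaries test no hypothesis, compare no regimens, and are internally consistent as specified. Most of this stands, and it keeps the point small. It does not correct the stated rates: the censored count mixes deaths with ongoing cases, and the fatal-event tables are not linked to the resolution curve.

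A reader might infer four stronger points that the documents do not support:

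- *That fatal events are recorded as resolved.* Censoring records no one as resolved; it gives them a future chance of resolving.
- *That the rule targets fatal adverse events.* It covers death from any cause, for example lymphoma progression with a lingering rash, and only where the end date is missing.
- *That a gap such as 100% against 80% is to be expected.* That needs one in five to die unresolved, a share found nowhere in the documents, and it appears only at the end of the curve.
- *That time to onset has the same error.* There, participants without the event "will be right-censored at the earlier of 30 days after the last dose date and date of last study visit". A treatment-emergent event must fall within 30 days of the last dose (SAP 9.2.1), so this describes risk while exposed, which is defensible. The life-table output is defined as a conditional proportion per interval, not a cumulative proportion, and crude incidence is tabulated alongside.

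**Conclusion.** The point holds for the resolution and improvement summaries. As specified, one minus Kaplan-Meier is at or above the true cumulative incidence of resolution. The two are equal only if nobody dies unresolved while others with the event could still resolve later. Under the assumptions above, shares of 2% to 10% dying unresolved overstate the day-90 rate by about 2 to 9 points and shorten the median by less than 1 day; at 20% the figures are about 19 points and 1.8 days. The late timepoint rates carry most of the bias. If few participants die with these events unresolved, the effect will be negligible. This is a worthwhile improvement to a descriptive safety summary and has no bearing on the primary analysis.

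**What to change.** In SAP 9.2.2:

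1. Treat death with the event unresolved as a competing event, in both the serious and non-serious branches. Report the Aalen-Johansen cumulative incidence of resolution or improvement at the selected timepoints, with confidence intervals suited to that estimator and the median read from the same curve. Keeping deaths in the risk set as never resolved is equivalent only if each is held to their own administrative censoring time.
2. State that a fatal outcome, or an end date equal to the date of death, is never counted as resolution or improvement, and confirm how end dates of fatal events are recorded.
3. In the summary table, show deaths with the event unresolved separately from other censoring.

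The cost is a different standard procedure on the same data, plus a check of how fatal events are entered. Reported resolution rates will be slightly lower if any participants die unresolved. The time-to-onset analyses need no change on this account.

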6.4. Follow-Up

6.4.1. Safety Follow-Up

The safety follow-up period is the interval between the EOT visit and the scheduled follow-up visit, which should occur 30 to 35 days after the EOT visit (or after the last dose of study treatment if the EOT visit was not performed). Adverse events and SAEs must be reported up until at least 30 days after the last dose of study treatment, the date of the follow-up visit, or until toxicities resolve, return to baseline, or are deemed irreversible, whichever is longer. Reasonable efforts should be made to have the subject return for the follow-up visit and report any AEs that may occur during this period.

If a subject is scheduled to begin a new anticancer therapy before the end of the safety follow-up period, then the safety follow-up visit should be performed before new anticancer therapy is started. Once new anticancer therapy has been initiated, the subject will move into the survival follow-up period.

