The occurrence of AEs should be sought by nondirective questioning of the subject during the screening process after signing the ICF and at each visit during the study. Adverse events may also be detected when they are volunteered by the subject during the screening process or between visits, or through physical examination, laboratory test, or other assessments. To the extent possible, each AE should be evaluated to determine:

- The severity grade (CTCAE Grade 1 to 5).
- Whether there is at least a reasonable possibility that the AE is related to the study treatment: suspected (yes) or not suspected (no).
- The start and end dates, unless unresolved at final follow-up.
- The action taken with regard to study drug.
- The event outcome (eg, not recovered/not resolved, recovered/resolved, recovering/resolving, recovered/resolved with sequelae, fatal, unknown).
- The seriousness, as per serious adverse event (SAE) definition provided in Section 8.3.1.

Unlike routine safety assessments, SAEs are monitored continuously and have special reporting requirements (see Section 8.3.2).

All AEs should be treated appropriately. If an AE is treated with a concomitant medication or nondrug therapy, this action should be recorded on Adverse Event form and the treatment should be specified on the Prior/Concomitant Medications or Procedures and Non-Drug Therapy form in the eCRF.

Once an AE is detected, it should be followed until it has resolved or until it is judged to be permanent; assessment should be made at each visit (or more frequently if necessary) of any

changes in severity, the suspected relationship to the study drug, the interventions required to treat the event, and the outcome.

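### SAP 9.2.2 counts a non-serious AE resolution after end of treatment whenever it is dated but censors unresolved AEs at the safety window, which biases late Kaplan-Meier resolution rates upward

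*SAP*

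**What the plan says.** SAP 9.2.2 (Adverse Events of Special Interest) defines the longest duration of a TEAE of any grade as "the longest interval between the date of occurrence of a TEAE and the date of resolution". For Grade 3 or higher events the end point is improvement to Grade 2 or lower. Neither definition has an upper time limit.

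Censoring depends on the end date alone: "Participants who have missing end date of a TEAE at the time of analysis will be right-censored using the following algorithm". The censoring date is then set by group:

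- **Serious TEAE:** the earliest of data cutoff, study discontinuation and death.
- **Non-serious, still on treatment:** data cutoff.
- **Non-serious, treatment discontinued:** "then the participant will be censored at date of safety follow-up visit, or 35 days after the end of treatment visit". The later date applies, and the last dose stands in where no such visit took place. In addition, "the censored date will be truncated by the earlier date of data cutoff, study discontinuation, and death if beyond".

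That truncation is worded for the censoring date only. SAP 4.1.4 leaves a wholly missing AE end date unimputed, so the 9.2.2 rule governs. The outputs are a Kaplan-Meier median, and "Resolution/improvement rates at selected timepoints will also be provided".

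On collection, Protocol 6.4.1 has AEs reported to at least 30 days after the last dose, the follow-up visit, "or until toxicities resolve, return to baseline, or are deemed irreversible, whichever is longer". Protocol 8.1.2 says of a detected AE that "it should be followed until it has resolved or until it is judged to be permanent".

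The SAP does not state in words that late resolutions count. It follows from three features: an unlimited resolution date, censoring only when the end date is missing, and truncation of the censoring date alone.

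**The concern.** Take two discontinued participants, each with a non-serious AE still open when the safety window closes. One AE resolves 100 days after the end-of-treatment (EOT) visit; that participant stays at risk to that day and is an event. The other is still unresolved at 100 days; that participant is censored back at about 35 days. Membership of the risk set after the window therefore depends on the later outcome. Kaplan-Meier needs censoring that carries no information about the outcome, and in this group it does. An AE judged permanent is the clearest case: it is known not to resolve, yet it is handled as if its outcome were merely unobserved.

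The other two groups in 9.2.2 do not have this asymmetry. Nor does time to onset, where TEAEs count up to 30 days after the last dose and event-free participants are censored no later than that.

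At stake is the description of how long colitis, diarrhea and rash last, and Grade 3 or higher febrile neutropenia. SAP 11.2 says these duration summaries were added to understand the duration of class-effect AEs. The error goes in the drug's favour.

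**Working it through.** The documents state no resolution rate, AE duration or share of late resolutions, so there is no plan figure to reproduce. The check has two parts.

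**1. Hand example.** Ten non-serious AEs; EOT at AE onset, so the window closes at day 35. Four resolve by day 35, three resolve at days 60, 90 and 120, and three never resolve. At day 35 the unresolved proportion is 6/10 = 0.60 under either rule.

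- SAP rule: the three non-resolvers leave at day 35, so three remain at risk and all are events. Unresolved: 0.60 × 2/3 = 0.40, × 1/2 = 0.20, × 0 = 0. Resolution is 60%, 80% and 100% at days 60, 90 and 120.
- Non-resolvers kept at risk: 0.60 × 5/6 = 0.50, × 4/5 = 0.40, × 3/4 = 0.30. Resolution is 50%, 60% and 70%.

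**2. Simulation (200,000 AEs per scenario).** All inputs are assumptions: a share p never resolves; the rest resolve exponentially with median m; the gap from onset to EOT visit is exponential; data cutoff is 180 to 540 days after onset; no deaths. The true resolution by day t is (1 − p)(1 − 2^(−t/m)). For p = 0.20 at day 180:

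- m = 21: 0.80 × (1 − 2^(−180/21)) = 0.80
- m = 45: 0.80 × (1 − 2^(−4)) = 0.75

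Under the SAP rule, time = resolution date if it is recorded by cutoff; otherwise the earlier of EOT + 35 days and cutoff. Exempt AEs (serious, or participant on treatment) run to cutoff.

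| Scenario, p = 0.20 | True, day 180 | SAP rule | Excess (points) |
|---|---|---|---|
| m = 21, mean gap 14 days, none exempt | 80% | 99% | 19 |
| m = 45, mean gap 14 days, none exempt | 75% | 93% | 18 |
| m = 21, mean gap 14 days, half exempt | 80% | 86% | 6 |
| m = 45, mean gap 14 days, half exempt | 75% | 82% | 7 |
| m = 21, mean gap 125 days, 20% exempt | 79.8% | 82.8% | 3 |
| m = 45, mean gap 125 days, 20% exempt | 75.0% | 80.1% | 5 |

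*Never-resolving share.* With m = 21, gap 14 and none exempt, p = 0.10 or 0.30 gives true values of 90% or 70%, and the SAP rule reports about 99 to 100% for both. With no never-resolving AEs there is essentially no bias (87.7% against 87.5% in a run with m = 60 and cutoff 365 to 730 days).

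*Recording of late resolutions (m = 21).* If half are recorded, the SAP value is still 99% with none exempt, but 83% with half exempt and 81.4% with the 125-day gap. If none is recorded, the SAP rule and a common cut-off are the same rule, so the asymmetry disappears.

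*Median time to resolution.* For m = 21 it is 29.7 days under both truth and the SAP rule. For m = 45 it is 58 against a true 64 days (gap 14, none exempt) or 62.5 against 63.5 (gap 125). It moves materially only with slower resolution: for m = 60 with cutoff 365 to 730 days, gap 14 and none exempt, 72.9 against 84.9 days (p = 0.20) and 79.9 against 108.3 (p = 0.30).

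*One common cut-off.* For m = 21, p = 0.20, gap 14 and none exempt, days 60/90/180 are 68.9/75.8/79.8% true, 73.7/88.5/99.4% under the SAP rule and 68.9/75.6/79.4% with one cut-off.

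**The case against.** The strongest reply is that the large figures are a worst case. In the earlier monotherapy study (Protocol 1.3), diarrhea occurred in 35% of 72 subjects, about 25; five had serious diarrhea and three discontinued for it. Protocol 5.4.2 manages diarrhea and colitis largely by interruption and restart, and expected treatment is about 14 months. Many of these AEs should therefore resolve on treatment or long before EOT. This stands, and it is why the 125-day gap with 20% exempt (5/25) is in the table. It is not decisive: Protocol 5.5.1 withdraws subjects whose AE delays therapy beyond 14 days unless the sponsor approves longer, so persistent AEs may have short gaps.

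Second, late resolutions may be poorly captured. Table 6 of the protocol schedules AE assessment only through the safety visit, and 6.4.1 moves subjects to survival follow-up once new anticancer therapy starts. The follow-up duty in 6.4.1 and 8.1.2 makes some late dates likely, but how many is unknown. The SAP's censoring date also has a rationale: it is about when the last scheduled AE assessment falls.

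Third, Grade 3 or higher summaries are less exposed, because 8.1.2 closes an AE record at each change of severity and so supplies an end date without full resolution. Numbers resolved and censored are reported beside the curve, and the timepoints are not fixed.

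A reader might infer that the reported curve drifts to 100%, or that AE durations in general read too short. The documents support neither. Unresolved serious AEs, and those in participants still on treatment, stay at risk beyond the safety window and hold the curve down: with m = 60, p = 0.20, 30% on treatment and 20% serious, day 360 is 87.9% against a true 78.8%. Typical durations hardly change when AEs resolve within weeks.

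**Conclusion.** The rule is inconsistent and should be corrected. For non-serious TEAEs after treatment discontinuation, censoring past the safety window depends on the outcome. Resolution and improvement rates beyond that window are biased upward if some AEs never resolve and some late resolutions are recorded.

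The direction follows from the text; the size rests on assumptions. With 20% never resolving, the day-180 excess is about 3 to 7 points in the mixed scenarios and about 19 points if every AE is non-serious and off treatment with EOT soon after onset. It grows with the never-resolving share and is nil if late resolutions are not recorded. The median is unchanged for AEs that resolve within weeks and shifts by no more than about six days at m = 45; larger shifts need resolution as slow as m = 60.

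The simulations draw the EOT gap independently of resolution time, which may not hold if persistent AEs cause discontinuation. Only Table 3.2.29 and Figure 4.5.2 are affected. They are descriptive; ORR, DOR, PFS and OS are untouched.

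**What to change.** Add one sentence to SAP 9.2.2: for participants who discontinued treatment and have a non-serious TEAE, a resolution or improvement dated after the later of the safety follow-up visit and 35 days after the EOT visit (with the existing truncation and the existing last-dose fallback) is censored at that date. Keep the later resolution dates in the AE listings.

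The work is that sentence and one line of derivation code for Table 3.2.29 and Figure 4.5.2; no new data are needed. The cost is that a few observed late resolutions no longer count as events, and late timepoints have few participants at risk. For m = 60, p = 0.20, gap 14 and none exempt, the common cut-off gives 67.3% at day 180 against a true 70.1%, so rates far beyond the window should be read with the numbers at risk.

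Censoring unresolved AEs at the last date they were known to be ongoing would keep the late resolutions, but it needs an assessment date that the documents do not define.
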